10.2.2 Participants

10.2.2.1 Participants for the main analysis

For data extraction and the creation of study cohorts, a sequential approach will be used as presented in Figure 4 and detailed below. This approach applies to the creation of the cohorts for the main analyses of the primary, secondary, and exploratory objectives.

	Data extraction	
STEP 1	Overall SOURCE population Inclusion criterion: Patients with SLE diagnosis in the study time period	
	Pool of patients exposed and unexposed to anifrolumab from the	overall source population
STEP 2	 STEP 2a: Exposed patients in the SOURCE population Inclusion criteria: First prescription of anifrolumab in the study period (index date) Other inclusion criteria^a 	 STEP 2b: Unexposed patients in the SOURCE population^b Inclusion criteria: Not exposed to anifrolumab Other inclusion criteria are not assessed at this step^b
	Exposed patients in the outcome-specific SOURCE population	
STEP 3	3a. Exposed in the Malignancy 3b. Exposed in the Serious SOURCE population Infection SOURCE population Malignancies' exclusion criteriac Serious infections' exclusion criteriac	ad
	Time-based exposure sets	
	4a. Malignancies' exposure set Patients exposed to anifrolumab (STEP 3a) + Unexposed patients (STEP 2b)	 4b. Serious infections' exposure set Patients exposed to anifrolumab (STEP 3b) + Unexposed patients (STEP 2b)
STEP 4	 Inclusion criteria for unexposed Similar duration of previous exposure to SLE SOC as the anifrolumab patient, at index date No prescription for anifrolumab prior to index date 	 Inclusion criteria for unexposed Similar duration of previous exposure to SLE SOC as the anifrolumab patient, at index date No prescription for anifrolumab prior to index date
	•Other inclusion criteriaª	•Other inclusion criteria ^a
	 Exclusion criteria for unexposed: Malignancies' exclusion criteria^c 	 Exclusion criteria for unexposed: Serious infections' exclusion criteria^d
	STUDY population (for each exposed patient, up to 3 unexposed patient)	nts are selected with the closest PS)
STEP 5	STUDY cohort for Malignancies	STUDY cohort for Serious Infections
	Malignancy cohort = malignancy_exposed + malignancy_unexposed	SI cohort = infection_exposed + infection_unexposed

Figure 4 Overview of the data extraction and definition of the study populations

PS: Propensity-Score; SLE: systemic lupus erythematous; SI: serious infection; SOC: standard of care. ^aOther inclusion criteria:

- A minimum data availability of 12 months prior to index date.
- Age ≥ 18 years, at index date.
- SLE severity: patients with moderate to severe SLE at index date.
- SLE activity: patients with at least a flare in the 6 months prior to index date.

^bInclusion and exclusion criteria for unexposed patients can only be applied at the creation of the exposure sets (STEP 4) because the time scale will be defined on the SLE duration of the exposed patients. Comparators do not have an index date before the identification of eligible anifrolumab patients.

^cMalignancies' exclusion criteria:

• A diagnosis of any malignancy prior to index date.

^dSerious infections' exclusion criteria

- A diagnosis of any malignancy prior to index date.
- A diagnosis of HIV/AIDS or congenital immunodeficiency prior to index date.
- Organ or bone marrow transplant prior to index date.
- Serious infection in the previous 6 months.

STEP 1 (Data extraction) – Overall source population

Inclusion criteria:

• Patients with SLE diagnosis (10th Revision International classification of diseases [ICD-10] codes M32.X) in the study time period.

STEP 2 – Identification of patients exposed and unexposed to anifrolumab in the overall source population

From the overall source population, exposed patients are selected. All patients not exposed to anifrolumab remain eligible to be comparators. Patients who are later exposed to anifrolumab are eligible to be comparators until then.

Step 2a. Exposed patients in the source population

Inclusion criteria:

- First prescription of anifrolumab in the study period (no anifrolumab prescription prior to index date): date of first anifrolumab prescription will be the **index date**.
- A minimum data availability of 12 months prior to index date.
- Age ≥ 18 years at index date.
- SLE severity (based on the SLE severity algorithm, Section 10.3.3.3): patients with moderate to severe SLE at index date³.
- SLE activity (based on the SLE activity algorithm, Section 10.3.3.3): patients with at least a flare (uncontrolled SLE) in the 6 months prior to index date.

Step 2b. Unexposed patients in the source population

Inclusion and exclusion criteria for unexposed patients can only be applied after identifying eligible exposed patients (at step 4) because unexposed patients do not have an index date before that (the time scale will be defined on the SLE duration of the exposed patients).

STEP 3 – **Identification of patients exposed to anifrolumab for the outcome-specific source** population

At step 3, the malignancy and serious infection source populations will be created.

Step 3a. Exposed patients in the malignancy source population

Additional exclusion criteria to be applied to the exposed patients:

• A diagnosis of any malignancy prior to index date.

³ According to the SLE severity algorithm, most moderate to severe patients will be those with a previous exposure to SOC indicated for moderate to severe disease. A very small group of patients, defined as having moderate/severe SLE based on the existence of SLE-related comorbidities, will not have a prescription of SOC for moderate/severe SLE.

Step 3b. Exposed patients in the serious infection source population

Additional exclusion criteria to be applied to the exposed patients:

- A diagnosis of any malignancy prior to index date.
- A diagnosis of HIV/AIDS or congenital immunodeficiency prior to index date.
- Organ or bone marrow transplant procedure prior to index date.
- A diagnosis of serious infection in the previous 6 months.

STEP 4 – **Time-based exposure sets**

This step is defined to create the time-based exposure sets, from the outcome-specific source populations. For each patient exposed to anifrolumab (identified in steps 3a and 3b) all unexposed patients from the source population (step 2b) that meet the following criteria will be included as unexposed patients.

Step 4a. Malignancy time-based exposure set

Patients exposed to anifrolumab from the malignancy source population (step 3a) and patients unexposed to anifrolumab (step 2b). Inclusion criteria for patients unexposed to anifrolumab (exposed to SLE SOC):

- At least a prescription of SOC indicated for moderate to severe SLE (Table 14).
- Duration of the previous exposure to SLE SOC similar to the SLE SOC duration of the corresponding exposed patient (+/- 45 days [wider time intervals may be considered if matches cannot be obtained using this time window]), at index date. The **index date** for the patient unexposed to anifrolumab will be the SLE SOC prescription date that will result in length of the SLE SOC treatment closer to SLE SOC treatment of the corresponding exposed patient.
- No prescription for anifrolumab prior to index date.
- A minimum data availability of 12 months prior to index date.
- Age ≥ 18 years at index date.
- SLE severity (based on the SLE severity algorithm, Section 10.3.3.3): patients with moderate to severe SLE at index date.
- SLE activity (based on the SLE activity algorithm, Section 10.3.3.3): patients with at least a flare (uncontrolled SLE) in the 6 months prior to index date.

Exclusion criteria for patients unexposed to anifrolumab (exposed to SLE SOC):

• A diagnosis of any malignancy prior to index date.

Step 4b. Serious infections' time-based exposure set

Patients exposed to anifrolumab from the serious infection source population (step 3b) and patients unexposed to anifrolumab (step 2b). Inclusion criteria for patients unexposed to anifrolumab (exposed to SLE SOC):

- At least a prescription of SOC indicated for moderate to severe SLE (Table 14).
- Duration of the previous exposure to SLE SOC similar to the SLE SOC duration of the corresponding exposed patient (+/- 45 days, [wider time intervals may be considered if matches cannot be obtained using this time window]), at index date. The **index date** for the patient unexposed to anifrolumab will be the SLE SOC prescription date that will result in length of the SLE SOC treatment closer to SLE SOC treatment of the corresponding exposed patient.
- No prescription for anifrolumab prior to index date.
- A minimum data availability of 12 months prior to index date.
- Age ≥ 18 years at index date.
- SLE severity (based on the SLE severity algorithm, Section 10.3.3.3): patients with moderate to severe SLE at index date.
- SLE activity (based on the SLE activity algorithm, Section 10.3.3.3): patients with at least a flare (uncontrolled SLE) in the 6 months prior to index date.

Exclusion criteria for patients unexposed to anifrolumab (exposed to SLE SOC):

- A diagnosis of any malignancy prior to index date.
- A diagnosis of HIV/AIDS or congenital immunodeficiency prior to index date.
- Organ or bone marrow transplant procedure prior to index date.
- A diagnosis of serious infection in the previous 6 months.

STEP 5 – **Propensity score matching to define the study populations**

From the malignancy and serious infection time-based exposure sets, the respective study cohorts will be created. For each exposed patient, up to three unexposed patients (exposed to SLE SOC) with the closest PS are selected to create the final combinations of exposed-unexposed patients.

For the purpose of the evaluation of malignancies as composite outcome (primary outcome) and separately for specific types of malignancies (secondary outcomes), the *Malignancy* cohort will include sub-cohorts defined by the exposure to anifrolumab (exposed or unexposed to anifrolumab): *malignancy_exposed and malignancy_unexposed* (Table 4).

For the purpose of the evaluation of serious infections as composite outcome (primary outcome), separately for opportunistic serious infections, other serious infections, pneumonia (overall), fatal and non-fatal pneumonia (secondary outcomes), and to evaluate the risk of recurrent infections leading to hospitalisation (exploratory outcomes), the *serious infection* cohort will include sub-

cohorts defined by the exposure to anifrolumab (exposed or unexposed to anifrolumab): *infection exposed and infection unexposed* (Table 4).

Objective	Main features	Input	Sub-cohorts'
Objective	Main leatures	cohort/population	abbreviation ^a
Primary cohort malignar	y_unexposed)		
Primary objective 1	Estimate the incidence of new	Malignancy	malignancy_exposed
Secondary objective 6	malignancies outcome (composite	cohort	malignancy_unexposed
	and separately).		
Primary objective 2	Estimate hazard ratio of new		
Secondary objective 7	malignancies outcome (composite		
	and separately).		
Secondary objective 5	Describe cohort demographic and		
	clinical characteristics.		
Primary cohort serious in	nfections (infection_exposed + infection	n_unexposed)	
Primary objective 3	Estimate the incidence of serious	Serious infection	infection_exposed
Secondary objectives 8, 9	infections outcome (composite and	cohort	infection_unexposed
	separately).		
Exploratory objective 11	Estimate the incidence of all		
	infections leading to hospitalisation		
Primary objective 4	Estimate hazard ratio of serious	1	
Secondary objective 10	infections outcome (composite and		
	separately).		
Exploratory objective 12	Estimate hazard ratio of all infections		
	leading to hospitalisation		
Secondary objective 5	Describe cohort demographic and]	
	clinical characteristics.		

Table 4 Cohorts, sub-cohorts by objective

^aExposed and unexposed defined by the exposure to anifrolumab: exposed or unexposed to anifrolumab, respectively.

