8.4 Malignancies and knowledge gaps

Published studies have identified an increased frequency of some malignancies among patients with SLE, particularly for non-Hodgkin's lymphoma, leukaemia, and cancer of the vulva, lung, thyroid, and liver [13]. Although there is a decreased risk of other select types of cancer in patients with SLE, the overall cancer risk in SLE is slightly greater as compared with the general population [13]. Possible pathways linking SLE and malignancies include inherent immune system abnormalities, SLE medication exposures, interactions between medication and viral exposure, co-existing conditions (such as Sjögren's syndrome) and presence of "traditional" risk factors for malignancy (such as smoking, obesity and reproductive history) [10, 52, 59, 103].

Treatments that induce immune suppression may impair immune surveillance and thereby increase the risk for initiation or growth acceleration of malignancies. Furthermore, Type 1 IFNs may play a role in tumour surveillance. Therefore, while blocking type 1 IFN might be beneficial in controlling autoimmune diseases, the same pathway of suppression could potentially increase the risk of malignancies.

The impact of treatment with anifrolumab on the potential risk of malignancies is not known. In the placebo-controlled clinical trials, at any dose, malignant neoplasms (including non-melanoma skin cancers) were reported in 1.3% patients receiving anifrolumab, compared to 0.6% patients receiving placebo [92]. Malignancies excluding non-melanoma skin cancers were observed in 0.7% and 0.6% of patients receiving anifrolumab and placebo, respectively. In patients receiving anifrolumab, breast and squamous cell carcinoma were observed in more than one patient [92].

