10.3.3.1 Potential confounders for the malignancy cohort

For the analysis of malignancies, potential confounders include demographics and lifestyle characteristics (as presented in Table 6), SLE history (including SLE severity, activity as detailed below) and other clinical characteristics. Some infections may be important risk factors for specific types of malignancies [6, 63] (Table 22), such as Human Papillomavirus (HPV) infection and the risk associated with cervical cancer [84] or the emergence of the oncogenic Epstein-Barr virus. HPV vaccine will be considered as reducing the risk of cervical, oropharyngeal, and anal cancer occurrence.

⁷Some data sources may not have available some of the relevant variables.

Comorbidities recognised as risk factors for cancer development will be considered, namely cardiovascular diseases [44, 45], diabetes [94], liver disease [87], kidney disease [86], chronic respiratory disease [25, 55], among others (Table 20). Likewise, several drugs have been associated with changes in the risk of cancer and will be included as covariates, namely antidiabetics [91], antihypertensives [20], antihrombotic agents [43, 53] and other recognised carcinogenic drugs (Table 24).

Furthermore, increased inflammatory activity is purported to be associated with malignancy risk. In addition to considering SLE severity and activity, other comorbidities may increase inflammatory status, namely other autoimmune diseases (excluding SLE), acquired immunodeficiencies, and chronic infections. Exposure to specific SLE drugs, such as prednisolone, cyclophosphamide, rituximab, azathioprine or cyclosporin, has also been purported to be associated with cancer development [3, 11, 100]. Adjustment for prior use of cyclophosphamide or rituximab are already taken into account when controlling the SLE severity as these drugs are used to define severe SLE. Within the group of other immunosuppressants, recognised carcinogenic drugs will be considered separately.

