	Pleuritis [51]	A15.6, A15.7, A16.5, A16.7
	Thrombocytopenia [51]	D69.6, D69.5, D69.4
Other comorbidities	Autoimmune diseases excluding SLE (e.g., rheumatological, inflammatory bowel disease and multiple sclerosis) [101] Immunodeficiencies (excluding congenital and HIV) [30]	L40, I73.0, M15.0, M35.0, K50, K51, G35 D80-D89
	Cardiovascular diseases (atrial fibrillation, coronary artery disease, hypertension) [46, 67, 81]	I48, I25.1, I10-I15
	Chronic respiratory diseases [30, 35, 67, 101]	J40-J47
	Gastrointestinal conditions (e.g., peptic ulcer disease, gastro- oesophageal reflux disease, dyspepsia, helicobacter pylori infection, Barrett's oesophagus, gastritis and duodenitis, chronic pancreas disease, chronic liver disease, gallstones)	K21, K22.7, K25-K29, K30, K76.9, K80-K82, K86, B98.0

Abbreviations: HIV, human immunodeficiency virus; ICD-10, international statistical classification of diseases tenth revision.

*Three variables were removed from the index because they are exclusion or censoring criteria: HIV, metastatic disease, any malignancy.

Table 21 Exemplar code list for SLE-related comorbidities (SLE severity and activity algorithms)¹¹

	Group	Conditions	ICD-10 codes
Moderate comorbid	Cardiovascular	Haemolytic anaemia	D55-D59
conditions	cardiorespiratory system	Myocarditis	I40
		Pericarditis	I30
		Pleurisy/pleural effusion	J90 J91
		Vasculitis (excluding aortitis)	M05.2
	Hepatic and	Acute pancreatitis	K85
	gastrointestinal	Hepatitis (non-viral)	K72.0
		Lupus enteritis/colitis	
	Musculoskeletal	Avascular ischaemic necrosis of bone	M87
	Neurological	Demyelinating syndrome/acute inflammatory demyelinating	G36-G37
		polyradiculoneuropathy	
		Mononeuropathy/polyneuropathy	G56-G64
		Myelopathy	G99.2
		Pseudotumor cerebri	G93.2
		Seizure	R56.8
	Renal	Nephritis	N10, N11
		Renal impairment (other than nephritis or end-stage renal disease)	S37.0, N18 (excl. N18.5)
	Ocular	Chorioretinitis	H30.9
		Episcleritis/scleritis	H15
Severe comorbid	Cardiovascular	Aortitis	I79.1
conditions	cardiorespiratory system	Arterial/venous thrombosis	I82
		Cardiac tamponade	I31.9
		Pulmonary haemorrhage	R04.8
		Stroke (cerebral infarction)	I63
		Transient ischaemic attack	G45
	Hepatic and gastrointestinal	Intestinal pseudo-obstruction	K56.0
	Neurological	Acute confusional state/psychosis	F05.1, F05.9
		Aseptic meningitis	G02.0, A87.0, G01
		Cranial neuropathy	S04

¹¹SLE severity and severity algorithms defined in Section 10.3.3.3 [39, 56].

	Group	Conditions	ICD-10 codes

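### The malignancy cohort neither excludes transplant recipients nor has a direct covariate for them, and congenital immunodeficiency is inconsistently specified, so the malignancy hazard ratio may carry residual confounding of unknown direction

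*Protocol*

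**What the plan says.** **Exclusions (Section 10.2.2.1).** For the malignancy cohort, Step 3a (exposed) and Step 4a (comparators) have one exclusion: "A diagnosis of any malignancy prior to index date". Figure 4 footnote c and the Table 2 rows for objectives 1, 2, 5a, 6 and 7 agree. The infection cohort (Steps 3b and 4b, Figure 4 footnote d) adds "A diagnosis of HIV/AIDS or congenital immunodeficiency prior to index date" and "Organ or bone marrow transplant procedure prior to index date", besides a recent serious infection. The protocol gives no reason specific to transplant or immunodeficiency for the difference.

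**Covariates.** Transplant is named in none of Tables 6, 20, 21, 22 and 24. Table 6 applies Table 20 to both cohorts. The Table 20 immunodeficiency row is labelled "Immunodeficiencies (excluding congenital and HIV) [30"], yet its code column gives D80-D89 without restriction. For malignancy, Section 10.3.3.1 names as sources of inflammation "namely other autoimmune diseases (excluding SLE), acquired immunodeficiencies, and chronic infections". The Table 20 footnote reads "Three variables were removed from the index because they are exclusion or censoring criteria: HIV, metastatic disease, any malignancy". In the malignancy cohort HIV is not an exclusion, but it does enter as a covariate through Table 22 (B20-B24).

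**Drugs.** Table 14 lists tacrolimus, cyclosporine, mycophenolic acid, sirolimus and azathioprine as SLE SOC, with no check on indication.

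**The concern.** Section 8.4 gives the protocol's own reasoning: "Treatments that induce immune suppression may impair immune surveillance and thereby increase the risk for initiation or growth acceleration of malignancies". Transplant recipients are a group in whom such treatment would be expected, and the protocol sets them aside for one primary outcome but keeps them for the other.

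The listed drugs also have an anti-rejection use (general pharmacology, not stated in the protocol). In a patient with an M32 code, an anti-rejection prescription can therefore meet the SOC requirement for a comparator, set that comparator's index date and prolong the SOC episode. The data sources can rarely separate the two uses. Under Section 10.4.1, drug indication is inpatient-only in France, absent in Germany, limited to a few drugs in Spain and not compulsory in the Danish prescription register.

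The balance checks (Section 10.7.1.1, step 10) and the outcome-model correction for imbalanced variables (Section 10.7.1.4) act only on variables in the covariate set. A transplant imbalance would not be seen. At stake are the primary malignancy HR (objective 2) and the sub-type HRs (objective 7).

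**Working it through.** **1. The plan's own figure.** Section 10.5.2 requires 3,195 anifrolumab patients for 80% power at HR 1.5, with SD(HR) 0.2, 1:3 matching, 5 years of follow-up and 6.31 malignancies per 1000 person-years. The check was a random-effects meta-analysis of four sources with the Table 13 shares, a log-HR SD of sqrt(ln(1 + (0.2/1.5)²)) = 0.132, two-sided 0.05 and 20,000 runs. Binomial event counts stood in for the Weibull/Cox step. Power at 3,195 was 0.790 (DerSimonian-Laird) and 0.802 (REML). The stated figure reproduces.

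**2. Bias formula.** Let pE and pU be the shares of affected patients among exposed and comparators after matching, and r their malignancy rate ratio against other patients:

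observed HR = true HR × [1 + pE(r − 1)] / [1 + pU(r − 1)]

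The documents give none of pE, pU and r. All values below are assumptions.

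**3. All affected patients are comparators (pE = 0, true HR 1.5).** Power is from the REML version of step 1.

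| pU | r = 2 | r = 3 | r = 5 |
|---|---|---|---|
| 1% | 1.5/1.01 = 1.49, power 0.79 | 1.5/1.02 = 1.47, power 0.77 | 1.5/1.04 = 1.44, power 0.75 |
| 3% | 1.5/1.03 = 1.46, power 0.76 | 1.5/1.06 = 1.42, power 0.70 | 1.5/1.12 = 1.34, power 0.60 |
| 5% | 1.5/1.05 = 1.43, power 0.72 | 1.5/1.10 = 1.36, power 0.63 | 1.5/1.20 = 1.25, power 0.45 |

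**4. Other distributions.**
- Partial imbalance (pE = 1%, pU = 3%): 1.47, 1.44 and 1.39 for r = 2, 3 and 5.
- Equal shares (2% and 2%): 1.50 for every r.
- Reverse imbalance (pE = 3%, pU = 1%): 1.5 × 1.03/1.01 = 1.53, 1.5 × 1.06/1.02 = 1.56 and 1.5 × 1.12/1.04 = 1.62.

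**5. What the PS captures indirectly.** SOC type and duration (Table 6, Section 10.9), the severity components including end-stage renal disease and renal failure (Section 10.3.3.3, Table 21) and chronic renal failure (Table 20) all enter. They do not identify transplant:
- severity is read over only 12 months before index, so an older end-stage renal code can be missed;
- matching on mycophenolate or tacrolimus use can pair a lupus patient with a transplant recipient;
- no calliper is set by default; Section 10.7.1.2 mentions one only as a possible later change.

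**6. Room to exclude.** Table 8 expects 3,506 initiators: 3,506 − 3,195 = 311, and 311/3,506 = 8.9%. Removing 1%, 3% or 5% leaves 3,471, 3,401 or 3,331. The projection in Appendix 4.3 has no step for prior malignancy, absence of a flare or lack of a match, so those losses draw on the same 8.9%.

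**The case against.** A reader might infer that these patients are wholly unadjusted and that they will mask a malignancy signal. The documents support neither.

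- **Adjustment.** The PS covers the routes by which transplant would act on treatment choice: the drugs themselves, their duration and renal disease. Section 10.3.3.1 also treats carcinogenic immunosuppressants separately. This stands as partial adjustment, with the gaps in step 5.
- **Direction.** That anifrolumab is not indicated in severe active lupus nephritis (Section 10.9) suggests fewer transplant recipients in the exposed arm. The same paragraph says such patients are kept and that nephritis manifestations enter the severity algorithm and the PS. No passage says that transplant recipients do not receive anifrolumab.
- **Entry.** Steady anti-rejection therapy alone does not qualify a comparator. Step 4a also requires a flare within 6 months, and a drug counts as initiated only if its class was not filled in the preceding 60 days. This stands, but the bar is low: Section 10.3.3.3 also accepts NSAID use or an emergency visit or admission for an SLE-related comorbidity.
- **Congenital immunodeficiency and HIV.** Table 20 contradicts itself on congenital disease rather than clearly omitting it, and its codes are exemplars to be finalised in the SAP. HIV is recovered through Table 22, so the footnote does no harm to adjustment.
- **Design intent.** Section 10.1 says that separate cohorts with outcome-specific criteria maximise sample size. That is a fair reason for not excluding these patients, but not for leaving out a covariate.

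**Conclusion.** The point holds as a gap in confounding control. Transplant recipients remain in the malignancy cohort without a direct covariate, the proxies are partial, and the planned diagnostics would not reveal an imbalance. Congenital immunodeficiency is inconsistently specified.

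Size and direction are not established. Under the assumptions of comparator shares of 1-5%, no exposed patients affected and rate ratios of 2-5, a true HR of 1.5 reads 1.49 to 1.25, and power at 3,195 falls from 0.80 to between 0.79 and 0.45. The lower end is negligible and the upper end is material. These figures allow nothing for balancing by the PS proxies, and they vanish with equal shares or reverse with the opposite imbalance. Either error would matter in a safety study.

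**What to change.** 1. Add prior organ or bone-marrow transplant and congenital immunodeficiency to Tables 6 and 20 as PS covariates for the malignancy cohort, using the definitions the infection cohort already needs, and report their balance before and after matching.
2. Reconcile the Table 20 immunodeficiency label with its D80-D89 codes, and reword the footnote so that HIV is called an exclusion for the infection cohort only, with a pointer to Table 22 for malignancies.
3. Add to Section 10.7.1.7 a malignancy sensitivity analysis without these patients. Alternatively, apply the exclusion in Steps 3a and 4a, with Figure 4 footnote c and Table 2 (objectives 1, 2, 5a, 6 and 7) changed to match.

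The covariates and the sensitivity analysis cost slight extra analysis work. Outright exclusion costs a small loss of patients, within the 8.9% margin on the projected count, and malignancy results that no longer cover transplant recipients. The covariates with a sensitivity analysis are therefore the better first choice.
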